7.8.3. Vital Signs

Summary tables for vital signs and their change from baseline will be presented for each scheduled time point by cohort. All vital sign data will be listed by subject and time of measurement.

7.8.4. Electrocardiogram (ECG)

The number and percentage of subjects with ‘normal’, ‘abnormal, not clinically significant’ and ‘abnormal, clinically significant’ ECG results will be summarized at baseline and each post-baseline time point.

All ECG data will be listed by subject and time of measurement.

The actual value of QTcF at each time point and change from baseline at each post-baseline time point will be summarized by cohort. Additionally, the number and percentage of subjects in each treatment group who meet any of the following criteria for QTcF will be tabulated.

- Maximum value > 450 to 480 msec
- Maximum value > 480 to 500 msec
- Maximum value > 500 msec
- Maximum increase from baseline > 30 to 60 msec
- Maximum increase from baseline > 60 msec

7.8.5. Physical Exam

Physical examination results including liver and spleen assessments will be listed for all subjects.

7.9. Other Analyses

7.9.1. Eastern Cooperative Oncology Group (ECOG) Performance Status

ECOG Performance Status will be performed pre-dose on Cycle 1 Day 1, Cycle 2 Day 1, every 3 cycles (3, 6, 9, 12+) Day 1 and 30 days post-last treatment. The number and percentage of subjects in each category will be summarized at each visit by cohort. All results will be listed.

7.9.2. Global Health Assessments

Global Health Assessments will be performed pre-dose on Cycle 1 Days 1, 8 and 15, Cycle 2 Day 1, every 3 cycles (3, 6, 9, and 12+) Day 1, and 30 days post-last treatment. The Global Health Assessment asks patients to rate their level of health today on a scale of 0 (the worst state

of health you can imagine) to 10 (the best state of health you can imagine). Descriptive statistics for Global Health Assessments score at each visit and the change from baseline at each post-baseline visit will be summarized at each visit and the change from baseline at each post-baseline visit by cohort. All data will be listed.

8. CHANGES IN THE PLANNED ANALYSESE

There are several changes in this version of SAP (v2.0) from the analyses specified in the protocol (amendment #9 dated 29-Oct-2019) due to data limitations as documented in the 13-601 Study Data Handling Document.

Most importantly, aggregated analyses of efficacy data are only limited to Phase 2a Cohort 1/2 FL patients and Cohort 5 PTCL patients. Efficacy data of all other patients will be for listing purposes only. In addition, lymph node response as a secondary endpoint in phase 2a is changed to dominant mass response in order to include both nodal and extra-nodal target lesions as measure of tumor burden.

In addition, AE severity grades in Phase 2a AE by grade analyses are mixture of the NCI CTCAE version 4.03 grading scales and the NCI CTCAE version 5.0 grading scales.

APPENDIX

A. Imputation of Missing or Partially Missing Dates

In general, missing or partial dates will be imputed at the data level. The following rules will apply for the specific analysis and summary purposes mentioned below only.

1. Prior/Concomitant Medications

When the start date or end date of a medication is partially missing, the date will be imputed to determine whether the medication is prior or concomitant. The following rule will be applied to impute partial dates for medications:

If start date of a medication is partially missing, impute as follows:

- If both month and day are missing, then set to Jan 01
- If only day is missing, then set to the 1st of the month

If end date of a medication is partially missing, impute as follows:

- If both month and day are missing, then set to Dec 31
- If only day is missing, then set to the last day of the month

If start/end date of a medication is completely missing, do not impute.

2. Adverse Events

When the start/end date of an AE is partially missing, the date will be imputed to determine whether the AE is treatment-emergent. When unable to determine, the AE will be considered as treatment emergent by default. The following rules will be applied to impute partial dates for AEs:

If start date of an AE is partially missing, impute as follows:

- If both month and day are missing, the imputed value will be Jan 1 or the first dosing date if they have the same year, whichever is later.
- If only day is missing, the imputed day will be the first day of the month or the first dosing date if they have the same month and year, whichever is later.
- If start date is completely missing, the imputed day will be the first dosing date as long as the AE end date is not before the first dosing date.

If the end date of an AE is partially missing, impute as follows:

- If both month and day are missing, the imputed value will be Dec 31
- If only day is missing, the imputed day will be the last day of the month
- If end date is completely missing, do not impute

3. Deaths

In case complete death dates are not recorded, impute as follows:

- If both month and day are missing, the imputed value will be Jan 1 or the last date of subject known to be alive+1, whichever is later.
- If only day is missing, the imputed value will be 1st of the month or the last date of subject known to be alive+1, whichever is later.

4. Subsequent Anti-cancer therapy

If the start day of a subsequent anti-cancer therapy is missing, it will be assumed to be the first day of the month.

5. Cancer Diagnosis

If a cancer diagnosis date is partially missing, impute as follows:

- If both month and day are missing, the imputed value will be Jan 1
- If only day is missing, the imputed day will be the first day of the month
- If end date is completely missing, do not impute

6. Prior Therapy/Response to Prior Therapy

If the day of a prior therapy or response to prior therapy date is missing, set it to 15th of the month. Otherwise, do not impute.

B. Pathology subgroup of Peripheral T-cell Lymphoma (PTCL)

CSR TFL Column	Pathology in EDC
AITL/TFH	AITCL
	PTCL Angioimmunoblastic T-Cell Lymphoma (AITL)
	PTCL with T-follicular helper phenotype
NOS	PTCL (Peripheral T-Cell Lymphoma) -NOS
Others	ATLL
	ATLL
	ATLL, HTLV-1 associated
	CD4+ PTCL, skin only
	CD4+ PTCL, skin-only
	Cutaneous Gamma Delta
	Cutaneous gamma-delta T-cell Lymphoma
	G/D TCL, skin and LN+
	HTLV-1 ATLL
	Hepatosplenic T cell Lymphoma
	Hepatosplenic T-cell Lymphoma
	LGL*
	Monomorphic Epitheliotropic Intestinal T-Cell Lymphoma
	NK/T-cell
	PTCL Anaplastic Large Cell Lymphoma (ALCL) ALK Negative (-)
	Primary Cutaneous Gamma/Delta T-cell Lymphoma
	T-Cell Prolymphocytic Leukemia
	T-cell prolymphocytic leukemia
	aggressive epidermotropic CD8+ **
	gamma-delta T-cell lymphoma
hepatosplenic T Cell lymphoma	
hepatosplenic gamma-delta T cell lymphoma	

*LGL (large granular lymphocytic leukemia) was miscategorized as PTCL at study entry

**CTCL with aggressive epidermotropic CD8+ was miscategorized as PTCL at study entry

C. Lugano Criteria for Response Assessments in NHL (Protocol Amendment 9 Table A4-11).

Response and Site	PET-CT–Based Response	CT-Based Response

Complete
 
Lymph nodes and extralymphatic sites
 
Nonmeasured lesion
 
Organ enlargement
 
New lesions
 
Bone marrow
	
Complete metabolic response
 
Score 1, 2, or 3^a with or without a residual mass on 5PS^b
 
It is recognized that in Waldeyer’s ring or extranodal sites with high physiologic uptake or with activation within spleen or marrow (e.g., with chemotherapy or myeloid colony-stimulating factors), uptake may be greater than normal mediastinum and/or liver. In this circumstance, complete metabolic response may be inferred if uptake at sites of initial involvement is no greater than surrounding normal tissue even if the tissue has high physiologic uptake.
 
Not applicable
 
Not applicable
 
None
 
No evidence of FDG-avid disease in marrow
	
Complete radiologic response (all of the following):
 
Target nodes/nodal masses must regress to < 1.5 cm in LDi No extralymphatic sites of disease.
 
Absent
 
Regress to normal
 
None
 
Normal by morphology; if indeterminate, IHC negative

Partial
 
Lymph nodes and extralymphatic sites
	
Partial metabolic response
 
Score 4 or 5^b with reduced uptake compared with baseline and residual mass(es) of any size:
 
At interim, these findings suggest responding disease.
 
At end of treatment, these findings indicate residual disease.
	
Partial remission (all of the following):
 
> 50% decrease in SPD of up to 6 target measurable nodes and extranodal sites.
 
When a lesion is too small to measure on CT, assign 5 mm × 5 mm as the default value.
 
When no longer visible, 0 × 0 mm.
 
For a node > 5 mm × 5 mm, but smaller than normal, use actual measurement for calculation.

Nonmeasured lesions
 
Organ enlargement
 
New lesions
 
Bone marrow
	
Not applicable
 
Not applicable
 
None
 
Residual uptake higher than uptake in normal marrow but reduced compared with baseline (diffuse uptake compatible with reactive changes from chemotherapy allowed). If there are persistent focal changes in the marrow in the context of a nodal response, consideration should be given to further evaluation with MRI or biopsy or an interval scan.
	
Absent/normal, regressed, but no increase.
 
Spleen must have regressed by > 50% in length beyond normal.
 
None
 
Not applicable

Response and Site	PET-CT–Based Response	CT-Based Response
No response or stable disease Target nodes/nodal masses, extranodal lesions Nonmeasured lesions Organ enlargement New lesions Bone marrow	No metabolic response Score 4 or 5 with no significant change in FDG uptake from baseline at interim or end of treatment Not applicable Not applicable None No change from baseline	Stable disease < 50% decrease from baseline in SPD of up to 6 dominant, measurable nodes and extranodal sites; no criteria for progressive disease are met No increase consistent with progression No increase consistent with progression None Not applicable
Progressive disease Individual target nodes/nodal masses Extranodal lesions Nonmeasured lesions	Progressive metabolic disease Score 4 or 5 with an increase in intensity of uptake from baseline and/or New FDG-avid foci consistent with lymphoma at interim or end-of-treatment assessment None	Progressive disease requires at least 1 of the following PPD progression: An individual node/lesion must be abnormal with: LDi > 1.5 cm, and Increase by > 50% from PPD nadir and an increase in LDi or SDi from nadir 0.5 cm for lesions < 2 cm 1.0 cm for lesions > 2 cm In the setting of splenomegaly, the splenic length must increase by > 50% of the extent of its prior increase beyond baseline (e.g., a 15-cm spleen must increase to > 16 cm). If no prior splenomegaly, must increase by at least 2 cm from baseline New or recurrent splenomegaly New or clear progression of preexisting nonmeasured lesions
New lesions	New FDG-avid foci consistent with lymphoma rather than another etiology (e.g., infection, inflammation). If uncertain regarding etiology of new lesions, biopsy or interval scan may be considered.	Regrowth of previously resolved lesions A new node > 15 cm in any axis A new extranodal site > 1.0 cm in any axis; if < 1.0 cm in any axis, its presence must be unequivocal and must be attributable to lymphoma Assessable disease of any size unequivocally attributable to lymphoma New or recurrent lymphoma

5PS = 5-point scale; CT = Computed tomography; FDG = Fluorodeoxyglucose; GI = Gastrointestinal; IHC = Immunohistochemistry; LDi = Longest transverse diameter of a lesion; MRI = Magnetic resonance imaging; PET = Positron emission tomography; PPD = Cross product of the LDi and perpendicular diameter; SDi = Shortest axis perpendicular to the LDi; SPD = Sum of the product of the perpendicular diameters for multiple lesion

a. A score of 3 in many patients indicates a good prognosis with standard treatment, especially if at the time of an interim scan. However, in trials involving PET where de-escalation is investigated, it may be preferable to consider a score of 3 as inadequate response (to avoid under treatment). Measured dominant lesions: Up to six of the largest dominant nodes, nodal masses, and extranodal lesions selected to be clearly measurable in two diameters. Nodes should preferably be from disparate regions of the body and should include, where applicable, mediastinal and retroperitoneal areas. Non-nodal lesions include those in solid organs (e.g., liver, spleen, kidneys, lungs), GI involvement, cutaneous lesions, or those noted on palpation. Nonmeasured lesions:

Any disease not selected as measured, dominant disease and truly assessable disease should be considered not measured. These sites include any nodes, nodal masses, and extranodal sites not selected as dominant or measurable or that do not meet the requirements for measurability but are still considered abnormal, as well as truly assessable disease, which is any site of suspected disease that would be difficult to follow quantitatively with measurement, including pleural effusions, ascites, bone lesions, leptomeningeal disease, abdominal masses, and other lesions that cannot be confirmed and followed by imaging. In Waldeyer's ring or in extranodal sites (e.g., GI tract, liver, bone marrow), FDG uptake may be greater than in the mediastinum with complete metabolic response, but should be no higher than surrounding normal physiologic uptake (e.g., with marrow activation as a result of chemotherapy or myeloid growth factors).

b. PET 5PS: 1, no uptake above background; 2, uptake < mediastinum; 3, uptake > mediastinum but < liver; 4, uptake moderately > liver; 5, uptake markedly higher than liver and/or new lesions; X, new areas of uptake unlikely to be related to lymphoma.

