7.8.2. Secondary Efficacy Endpoint

7.8.2.1. Progression free survival

Progression-free survival (PFS) is defined as the time from the start of study treatment to the first documentation of disease progression as assessed by investigator (see appendix C) or death from any cause, whichever occurs first.

Progression-free survival = (first documentation of disease progression or death – first dose date of study treatment + 1) /30.4375 in months.

PFS will be right censored for subjects who meet one of the following conditions: 1) no baseline disease assessments; 2) starting a new anti-cancer therapy before documented disease progression or death; 3) progression or death immediately after more than 6 months since the last disease assessment (or more than 12 months if beyond cycle 12); and alive without documented disease progression. The censoring convention follows the FDA guidance for Industry Clinical Trial Endpoints for the Approval of Cancer Drugs and Biologics (2018) and references within the guidance document. The censoring rules are summarized in Table 1.

Table 1. Date of Event or Censoring for PFS

Scenario	Date of PFS Event or Censoring	Outcome
Death or progression between the planned disease assessments	Date of death or first disease assessment showing PD, whichever occurs first	Event
Death before the first disease assessment	Date of death	Event
No baseline disease assessment	Date of first dose of study treatment	Censored
New anti-cancer treatment started	Date of last disease assessment prior to or on the date of new anti-cancer treatment	Censored
Death or progression immediately after missing more than 1 scheduled disease assessment ^[1]	Date of the last disease assessment before death or progression	Censored
Alive without documented disease progression	Date of last disease assessment	Censored

^[1] missing ≥ 6 months if in Cycle 1~12 or missing ≥ 12 months if beyond Cycle 12

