7.8.2.2. Duration of response

For responders (PR or better), duration of response (DOR) is defined as the time from the date of the earliest PR or better to the first documentation of disease progression or death from any cause, whichever occurs first. The censoring convention and analysis method of DOR will be the same as those for PFS in Section 7.8.2.1. DOR will be analyzed for subjects who achieved PR or better (i.e. responders only).

DOR = (first documentation of progression or death – the date of the earliest PR or better + 1) /30.4375 in months.

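### SAP Appendix A.4 moves a next-therapy start with a missing day to the 1st of the month without checking for a progression documented in that month, so some genuine PFS and DOR events would become censored

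*SAP*

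**What the plan says.** Appendix A.4 of the SAP has one rule: "If the start day of a subsequent anti-cancer therapy is missing, it will be assumed to be the first day of the month". It sets no lower bound. The appendix opens with "In general, missing or partial dates will be imputed at the data level" and then confines its rules to the analysis and summary purposes it names. A.4 names none.

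Neighbouring rules differ. For a death with a missing day (A.3), "the imputed value will be 1st of the month or the last date of subject known to be alive+1, whichever is later". For an adverse event start (A.2), "the imputed day will be the first day of the month or the first dosing date if they have the same month and year", again taking the later date. For earlier treatment (A.6): "If the day of a prior therapy or response to prior therapy date is missing, set it to 15th of the month".

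The SAP uses the next-therapy date in four places:

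- **PFS (7.8.2.1).** Censoring applies to patients "starting a new anti-cancer therapy before documented disease progression or death". Table 1 sets the censoring date as: "Date of last disease assessment prior to or on the date of new anti-cancer treatment".
- **DOR (7.8.2.2).** "The censoring convention and analysis method of DOR will be the same as those for PFS in Section 7.8.2.1".
- **Best overall response (7.8.1).** The window closes at the start of new therapy, if that comes before progression and data cutoff.
- **A listing (7.1.2)** for patients without enough information to evaluate response.

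**The concern.** Progression normally comes before the next treatment. Protocol 4.4.1 lists progression that requires other therapy as a reason to stop. When the two fall in one calendar month and only the month of the therapy is known, A.4 can reverse their order on paper. A documented progression is then treated as if it followed a change of therapy. The event is removed and follow-up is cut back to an earlier scan.

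At stake is the accuracy of the PFS and DOR curves for the FL patients (Cohorts 1 and 2) and PTCL patients (Cohort 5), the only groups with aggregated efficacy analyses. The A.2 and A.3 floors show that the authors guarded other imputed dates. A.1, A.5 and A.6 have no floor, but none of them decides between event and censoring.

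**Working it through.** The plan gives no figure for this rule, so there is none to reproduce. The check applies the rules to dates.

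**Inputs.** Cycles are 28 days (Protocol 7.3.3.1) and response is assessed every 3 cycles from Cycle 3 (Protocol 7.3.2, Appendix 1), so scans are 84 days apart. SAP 7.8.2.1 gives PFS in months as (event date − first dose date + 1)/30.4375. The lag from PD to next therapy and the share of missing days are not in the documents and are assumed.

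**Constructed patient.** First dose 1 January 2018; scans on 26 February (C3D1) and 21 May (C6D1). PD is found on 21 May. Next therapy truly starts on 28 May but is recorded only as May 2018.

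- True order: event, (140 + 1)/30.4375 = 4.63 months.
- With A.4: start imputed to 1 May, before the PD. PFS is censored at 26 February, (56 + 1)/30.4375 = 1.87 months.
- DOR, if response was first seen on 26 February: from an event at (84 + 1)/30.4375 = 2.79 months to censoring at 1/30.4375 = 0.03 months.
- Boundary: PD on 1 May stays an event, because the imputed start is not before it. PD on 2 May is censored.

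**Share of PDs lost, given a missing day.** With lag L and a month of m days, PD days 2 to m − L are lost, that is m − L − 1 days (or none if this is negative). Over 2016 to 2019 (1,461 days, 48 months):

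| Lag (days) | PD days lost | Share |
|---|---|---|
| 7 | 1,461 − 48×8 = 1,077 | 74% |
| 14 | 1,461 − 48×15 = 741 | 51% |
| 21 | 1,461 − 48×22 = 405 | 28% |
| 28 | 28×2 + 16×1 = 72 | 5% |

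The last row counts two days in each 31-day month and one in each 30-day month.

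**Direction.** Take 20 patients with events at months 1 to 20 and move the month-12 event to censoring at 6.5. Survival after month 6 is 14/20 = 0.700, and 13 rather than 14 remain at risk from 6.5.

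- S(10): 0.500 becomes 0.700×9/13 = 0.485.
- S(11): 0.450 becomes 0.700×8/13 = 0.431.
- S(12): 0.400 becomes 0.431.

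The curve dips between the new censoring date and the lost PD, and is higher from the lost PD onward.

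**Size per lost PD.** Kaplan-Meier simulation with exponential event times (median 6 or 12 months), 84-day scans and 15% of events as deaths. One lost PD raises the 12-month PFS rate by about 1.0 to 1.6 points with 40 patients. It raises the 12-month DOR rate by about 2.5 to 5.5 points with 12 to 16 responders (30 to 40% of 40). Median PFS at n = 40 was unchanged in 61% of cohorts (true median 6 months) and 42% (12 months); otherwise it rose, with a mean shift of 0.2 to 0.6 months.

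**How many are lost.** Illustration only: next therapy recorded for 50% of progressors, 20% of those with the day missing, 14-day lag. Then 0.50×0.20×0.507 = 5.1% of PDs, about 1.5 per 30. Under the same simulation assumptions the 12-month PFS and DOR rates each rise by 1.2 to 1.3 points. If every day is recorded, the effect is zero.

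**Scale.** The 95% half-width at a rate of 50% is 1.96×√(0.25/40) = 15.5 points for 40 patients, 24.5 for 16 and 28.3 for 12.

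**The case against.** The best counter-argument is scope. Appendix A restricts its rules to the purposes it names, A.4 names none, and SAP 7.1.2 mentions Appendix A date imputation only for adverse events and for prior or concomitant medications and procedures. On a literal reading, A.4 might not touch PFS at all. This stands as a gap in the text. But A.3, A.5 and A.6 name no purpose either, and BOR, PFS and DOR are the only analyses that use the next-therapy date. Use in censoring remains the natural reading.

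Second, A.3 is an imperfect precedent. Its floor prevents an impossible date, whereas therapy before documented PD is possible and is what the censoring condition is for. That is fair. With a missing day the true order within the month is unknown, and any rule will misclassify someone. The argument for a floor is that PD first is the usual order.

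Third, the effect may be negligible. The study ends at the visit 30 days after treatment (Protocol 3.1.3), which limits how many next therapies are recorded. The Study Data Handling Document cited in SAP 8 was not available and may hold a safeguard. Both points stand.

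A reader might infer that the rule can only inflate PFS and DOR. The example above shows otherwise: the curve can fall before the lost PD. A patient without PD who switches therapy can also lose a scan made between the 1st and the true start, which moves censoring earlier and lowers the curve slightly. A death without earlier PD is not wrongly lost, since therapy must have started before it.

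A reader might also see a conflict in Table 1 between the missed-assessment row and its 6- and 12-month footnote. The footnote defines that row and agrees with the text. Only the text's strict inequality against the footnote's ≥ differs, which is clerical and separate.

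**Conclusion.** The point holds in a limited form. Followed as written, A.4 together with 7.8.2.1 and 7.8.2.2 turns a genuine progression into censoring when three things coincide: the therapy day is missing, PD came first, and both fall in the same month with PD on day 2 or later. No other SAP text prevents this. The net tendency is upward for PFS and DOR from the lost PD onward.

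The shares of 74%, 51%, 28% and 5% are calendar arithmetic, conditional on a missing day and the assumed lag. The total effect cannot be computed from the documents. It may be zero, and in the illustrative case it is 1.2 to 1.3 points at 12 months, well inside the confidence intervals.

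The documents do not support a stronger conclusion. A reader might infer a threat to the trial's conclusions, but PFS and DOR are secondary and descriptive, and Protocol 11.1.3 sets no success criteria. The BOR window closes early by the same route, but ORR would change only if a first response and a new therapy fell in one month, which should seldom happen. The censoring convention itself is not in question. This is a cheap improvement.

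**What to change.** In Appendix A.4, state that the rule serves BOR, PFS and DOR, and replace the sentence with:

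> If only the start day is missing, impute the later of the 1st of the recorded month and the date of any PD documented in that same month and year.

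A PD on the imputed date stays an event, because censoring requires therapy to start before progression. In the constructed case PFS returns to an event at 4.63 months. No PD-first case is lost at any lag. Also report how many PFS, DOR and BOR outcomes depend on an imputed therapy date. If the Study Data Handling Document already has such a rule, citing it is enough.

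The cost is two sentences and three counts. PFS and DOR may come out slightly shorter. A true therapy-before-PD case with a missing day would count as an event whenever both dates share a month: 77%, 54%, 31% and 8% of such cases for gaps of 7, 14, 21 and 28 days (for 7 days, (1,461 − 48×7)/1,461). The documents do not say how common these are; the counts would show how many outcomes are open to the question.
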